# Patients who require a dose interruption lasting more than 21 consecutive days will be discontinued from the study.

Patients who are discontinued from the study should undergo an Early Termination Visit and subsequent Safety Follow-up Visit as appropriate per Section 7.3.1 Patient Withdrawal Procedures, and associated adverse events followed as described in See Section 10 Adverse Events.

Hematology and serum chemistry parameters will be assessed every 2 weeks for the first 8 weeks of the Treatment, and every 4 weeks thereafter for the remainder of the study. Prior to dose interruption, hematology parameters should be confirmed with repeat testing at an interval deemed appropriate by the Investigator (e.g., at the next protocol-defined visit or an Unscheduled Visit), except in severe cases where immediate interruption of dosing is necessary for the safety of the patient. Blood draws confirming dose interruption criteria should occur prior to the first daily dose on the day of draw.

Dose interruption requirements for hematologic abnormalities are provided below. However, less significant changes may warrant clinical intervention and the Investigator should use his/her best clinical judgment when considering a dose interruption whether for singular or aggregate hematology results above the limits provided in Table 3, or for other clinical signs, symptoms, or considerations that suggest dose interruption is in the best interest of the patient.

Table 3: Selected Hematologic Thresholds for Dose Interruption

Neutrophil Count	Dose Adjustment		
Less than 1 x 10  /L	Interrupt dose until recovered to greater than $1.5 \times 10^9$ /L and resume dosing at previous dose		
Female Hemoglobin Level	Dose Adjustment		
Less than 10 g/dL	Interrupt dose until recovered to greater than 11.5 g/dL and resume dosing at previous dose		
Male Hemoglobin Level	Dose Adjustment		
Less than 11.5 g/dL	Interrupt dose until recovered to greater than 13 g/dL and resume dosing at previous dose		
Platelet Count	Dose Adjustment		
Less than 75 x 10  /L	Interrupt dose until recovered to greater than 75 x 10  /L and resume dosing at previous dose		
Greater than 750 x 10  /L	Interrupt dose until recovered to less than 600 x 10  /L and resume dosing at previous dose		

Upon dose interruption, the parameters that triggered the interruption should be monitored at least weekly until either: 1) recovery above the threshold for dosing resumption is achieved, or 2) the allowable 21-day interruption has elapsed. In the case of severe neutropenia (neutrophil counts less than 0.5 x 10^9/L) patients should discontinue the study drug and receive instructions to seek medical help if they develop fever or signs of infection. Patients who discontinue the study due to lack of acceptable recovery of parameters within 21 consecutive day dose interruption period should continue to be monitored as appropriate through acceptable clinical resolution.

If the patient recovers above the threshold for interruption before the 21 consecutive day interruption period ends, they may remain in the study. Subsequent dose interruptions within a patient should be discussed with the Medical Monitor to determine continued participation in the study.

### 8.3. Treatment Compliance

At each scheduled study visit after randomization, the Investigator or designee will interview the patient regarding treatment compliance and compare the number of dispensed versus returned study drug tablets. Patients should strive for 100% compliance with the daily dosing schedule. Retraining on treatment compliance should occur for patients with less than 80% or over 120% compliance at any visit and the Sponsor should be notified.

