#### 8. DESCRIPTION OF STUDY TREATMENTS

### 8.1. Description of Treatments

In the Treatment Period, patients will be stratified by alopecia areata subtype and randomized to 1 of 2 CTP-543 treatment arms in a 1:1 ratio. Treatments arms will include:

- CTP-543 12 mg BID (1 x 12 mg and 1 x placebo tablet every 12 hours)
- CTP-543 24 mg QD (2 x 12 mg in the morning and 2 x placebo tablets in the evenings)

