#### 8.4.3. Study Drug Preparation and Administration

No study drug preparation is required. Patients will take the first dose of study drug in the clinic on Day 1 and will be instructed to take study drug approximately every 12 hours. Patients should dose study drug in the clinic on all Study Visit Days after clinical laboratory blood draws are completed.

Study drug should be taken at approximately the same times each day, with water, and consistently with or without meals. Patients should be instructed to take study drug as prescribed according to the Week, Day, and Time of day designations in the dosing card. If a dose is missed, the patient should not take two doses at the same time. The missed dose should be

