11 STUDY TREATMENT EXPOSURE AND TREATMENT COMPLIANCE

A summary of exposure to study drug (days) will be presented by dosing regimen based on the Safety analysis population. Exposure to study drug, in days, will be computed as follows:

[(Date of last dose of study drug – Date of first dose of study drug) + 1]

Compliance with study drug (%) will be calculated as follow:

Number of tablets taken x 100%
Total number of tablets planned to be taken

where the number of tablets taken is defined as the total number of tablets dispensed minus the total number of tablets returned, and total number of tablets planned to be taken is defined as the exposure to study drug multiplied by the number of planned tablets per dose (i.e., 2).

Descriptive statistics for the compliance to study drug will be presented by dosing regimen based on the Safety population. Frequency distribution will also be presented for the following categories: < 80%, 80% - 120%, and > 120%.

Exposure and compliance will be displayed in a listing of study treatment administration.

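### SAP 11 analyses compliance only as one pooled tablet percentage, which can stand for different active-drug intake in the two arms because every active QD tablet is in the morning dose

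*Protocol*

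**What the plan says.** Protocol 8.1 lists the two arms as "CTP-543 12 mg BID (1 x 12 mg and 1 x placebo tablet every 12 hours" and "CTP-543 24 mg QD (2 x 12 mg in the morning and 2 x placebo tablets in the evenings". Each patient therefore takes two tablets in the morning and two in the evening, and two of the four daily tablets are active.

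Protocol 8.3 assesses compliance at visits by interview and by asking sites to "compare the number of dispensed versus returned study drug tablets". It adds an action limit: "Retraining on treatment compliance should occur for patients with less than 80% or over 120% compliance at any visit". Protocol 8.4.3 tells patients to dose "according to the Week, Day, and Time of day designations in the dosing card", to skip a missed dose rather than make it up, and to discuss dosing deviations at each visit.

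SAP 11 defines the analysed variable: "the number of tablets taken is defined as the total number of tablets dispensed minus the total number of tablets returned". The denominator is "exposure to study drug multiplied by the number of planned tablets per dose (i.e., 2". The result is summarised by regimen with descriptive statistics and three categories: below 80%, 80% to 120%, and above 120%. Neither document defines a compliance variable that separates morning from evening tablets, or active from placebo.

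**The concern.** The stated objective (Protocol 6) is to compare two ways of giving the same 24 mg total daily dose, and the dose-selection rationale in Protocol 4.2.1 cites better adherence as a reason to study once-daily dosing. A reader of the study report will want to know whether the arms received similar amounts of active drug. Pooled compliance is the only planned analysis of intake that could answer this. The Schedule of Events has no pharmacokinetic sampling, and exposure in SAP 11 is only the number of days from first to last dose.

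The placebo layout that protects the blind makes the pooled percentage behave differently by arm. In the BID arm it follows active intake as long as whole doses are missed. In the QD arm it mixes a morning dose that carries all the drug with an evening dose that carries none. Two arms with the same compliance table could have received different amounts of drug, and nothing planned would show it.

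**Working it through.** **Inputs.** Tablets per dose and their content: Protocol 8.1. Treatment duration of 24 weeks, or 24 × 7 = 168 days: protocol synopsis. Compliance formula and categories: SAP 11. Missed doses not made up: Protocol 8.4.3.

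**1. The plan's own denominator.** SAP 11 gives 168 × 2 = 336 planned tablets. Protocol 8.1 gives 168 days × 2 doses × 2 tablets = 672. A fully adherent patient would score 672 / 336 = 200%. The SAP denominator therefore does not match the planned tablet count. That is a separate error, since it multiplies days by tablets per dose. All the steps below use the true count of four tablets a day, so the present point remains after the denominator is corrected.

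**2. Loss from one missed dose.**

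| Dose missed | Tablets returned, either arm | Active drug lost, BID | Active drug lost, QD |
|---|---|---|---|
| Morning | 2 | 12 mg | 24 mg |
| Evening | 2 | 12 mg | 0 mg |

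The tablet count is the same in every cell; the drug lost is not.

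**3. Formula.** Let *m* and *e* be the shares of morning and evening doses taken, each between 0 and 1. Assume whole doses are missed and there is no over-use. Pooled compliance is P = (m + e) / 2 in both arms.

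- BID active share = (m + e) / 2 = P.
- QD active share = m = 2P − e, which lies between max(0, 2P − 1) and min(1, 2P).

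**4. Range at the same pooled compliance.**

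| Pooled P | BID active share | QD active share, lowest to highest |
|---|---|---|
| 95% | 95% | 90% to 100% |
| 90% | 90% | 80% to 100% |
| 80% | 80% | 60% to 100% |
| 75% | 75% | 50% to 100% |

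At P = 80%, the lower action limit, the BID average is 0.80 × 24 = 19.2 mg/day. The QD range is 0.60 × 24 = 14.4 mg/day to 1.00 × 24 = 24 mg/day.

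**5. Less extreme patterns (assumed miss rates).** Pooled compliance is 80% in every row.

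| Morning missed | Evening missed | BID active share | QD active share |
|---|---|---|---|
| 20% | 20% | 80% | 80% |
| 10% | 30% | 80% | 90% |
| 30% | 10% | 80% | 70% |
| 2% | 38% | 80% | 98% |
| 38% | 2% | 80% | 62% |

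The gap is zero when misses are balanced, and it changes sign with the time of day at which they cluster.

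**The case against.** Several points on the other side are sound.

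- **Equal misses give equal intake.** The documents give no morning and evening miss rates. Tablets are identical and the blinded schedule is the same in both arms, so misses may well be balanced. A reader might infer that the same figure necessarily means different intake, or that QD patients will have received much less drug. Neither follows. The difference needs unequal miss rates, and if evenings are missed more often QD patients receive more drug than the pooled figure suggests.
- **The pooled count is not the only information collected.** Interviews and deviation discussions take place at visits, and the Study Manual and eCRF, which are not among the documents, may ask for more. This stands, but none of it feeds the variable defined in SAP 11.
- **The 60% and 100% ends are patient-level extremes.** They require every miss to fall at one time of day; an arm-level gap of that size would need the same pattern across many patients.
- **The BID figure assumes whole-dose misses.** If single tablets are missed, active and placebo cannot be told apart, and the bounds given for QD apply to BID as well.
- **The efficacy comparison is as randomized and for estimation only.** Compliance enters no efficacy model, and losing a full day's drug with one missed morning dose is partly a property of once-daily dosing. A reader might infer that the primary estimate is biased. It is not: it remains the estimate for the regimens as assigned.
- **The 80% retraining limit.** A reader might conclude that it fails in the QD arm. It concerns adherence to a blinded schedule that is the same in both arms, so it has the same behavioural meaning in each, and there is no case for changing it.

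What remains is that nothing planned would show whether misses were balanced.

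**Conclusion.** The point holds as a limitation of the planned compliance summary. At 80% pooled compliance the active share is 80% in BID and can lie between 60% and 100% in QD; at 90% it is 90% against 80% to 100%. These figures assume a correct denominator of four tablets a day, whole doses missed, and no over-use. The size of any real gap, and its direction, cannot be known from the documents.

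The consequence is confined to interpretation. Without a split by time of day, the report cannot say how much active drug each regimen delivered, and so cannot help a reader judge how far a difference in SALT response, or the lack of one, goes with the drug actually taken. Sample size and the primary estimate do not change. The improvement is worth making because it is cheap.

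**What to change.** **Data collection (Protocol 8.3 and eCRF).** At each accountability visit, record returned tablets separately for the AM and PM positions of the dosing card, for every patient in both arms. Both arms have two identical-looking tablets at each position, so this does not unblind. It assumes that returned cards show which positions are unused. Protocol 8.4.3 says only that the cards designate the time of day, so this should be confirmed against the Study Manual.

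**Analysis (SAP 11).** Keep the pooled percentage, with its denominator reconciled to the tablets planned in Protocol 8.1. Beside it, by regimen and with the same three categories, summarise:

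- AM compliance and PM compliance;
- active-drug compliance, derived after unblinding: AM compliance alone for QD, and the mean of AM and PM compliance for BID. State that the BID value is an approximation when single tablets are missed.

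Leave the retraining rule as it is.

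**Cost.** One extra count field per accountability visit, slightly more site time at drug return, an eCRF and protocol update with the IRB review that an amendment needs, and one extra table.

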### 8.4. Study Drug Materials and Management

Please consult the Study Manual for a complete description of the study drug and requirements for storage, handling, dispensing, accountability, returns and destruction.

#### 8.4.1. Physical Description of Study Drug

Study drug will be CTP-543, a deuterated analog of ruxolitinib or an identical placebo tablet. Details regarding formulation and dosage are presented in Table 4.

**Table 4:** Investigational Product

	Investigational Product (CTP-543 or Placebo)
Product Name:	CTP-543
Dosage Form:	Tablet
Dosage Strength of CTP-543	12 mg or placebo
Route of Administration	Oral
Physical Description	White, capsule-shaped tablets

### 8.4.2. Study Drug Packaging, Labeling, and Storage

CTP-543 active and placebo tablets will be packaged and labeled by an appropriately qualified vendor. Study drug will be dispensed at study visits as specified in the schedule of events (Table 1). To maintain the blind for investigators, subjects, and site personnel, subjects will take IP in the am and pm no matter which regimen they are assigned to:

- 12 mg BID (1 x 12 mg in AM + placebo; 1 x 12 mg in PM + placebo)
- 24 mg QD (2 x 12 mg QD in AM; 2 x placebo in PM)

Additional details on the packaging, labeling and dispensing instructions can be found in the Study Manual.

The label(s) for the investigational product will include sponsor name, address and telephone number, the protocol number, investigational product name, dosage form, amount of investigational product per container, lot number, unique dosing card number, storage conditions, and required caution statements and/or regulatory statements, as applicable. Additional information may be included on the label as applicable per local regulations.

Adequate supplies of study drug will be provided to each site. Study drug should be stored in the original package between 15°C to 25°C (59°F to 77°F), as stated on the product label, in a secure, temperature-monitored, locked area, under the responsibility of the Investigator or other authorized individual until dispensed to the patients.

Study drug dispensed to patients should be stored in the original package at room temperature as stated on the package label. No special handling procedures are required.

#### 8.4.3. Study Drug Preparation and Administration

No study drug preparation is required. Patients will take the first dose of study drug in the clinic on Day 1 and will be instructed to take study drug approximately every 12 hours. Patients should dose study drug in the clinic on all Study Visit Days after clinical laboratory blood draws are completed.

Study drug should be taken at approximately the same times each day, with water, and consistently with or without meals. Patients should be instructed to take study drug as prescribed according to the Week, Day, and Time of day designations in the dosing card. If a dose is missed, the patient should not take two doses at the same time. The missed dose should be

**Protocol CP543.2003** 

skipped and the patient should resume regular dosing at the next scheduled time. Deviations from prescribed dosing should be discussed at each visit for assessment of compliance and retraining when necessary.

#### 8.4.4. Study Drug Return and Disposal

The Sponsor (or designee) will review with the Investigator and relevant site personnel the process for study treatment return, disposal, and/or destruction, including responsibilities for the site versus the Sponsor (or designee). Specific requirements for destruction or return are defined in the Study Manual.

#### 8.4.5. **Study Drug Accountability**

To satisfy regulatory requirements regarding drug accountability, all study drug will be reconciled in full. The Investigator or designee must maintain accurate records of the receipt of study drug, including date received, lot number, amount received, condition of the package, and the disposition of study drug.

Current dispensing records will also be maintained, including the date and amount of medication dispensed to each individual patient. Returned study drug records will be maintained and final study drug reconciliation will also be recorded for each patient.

#### 8.5. **Concomitant Medications and Procedures**

All medications, including over-the-counter therapies (e.g., vitamins, herbal, and nutritional supplements), taken one month prior to Screening and through the Follow-up Visit will be recorded in the patient's source documentation and documented in the eCRF.

Any concomitant medication deemed necessary for the wellbeing of the subject may be given at the discretion of the Investigator. Use of medications that are prohibited per protocol may require patient withdrawal from the study.

The following treatments and procedures are not permitted during the study:

- Medications that may affect hair regrowth or immunosuppression (such as: corticosteroids administered orally, by injection, or applied to areas of skin affected by alopecia; topical application of anthralin, squaric acid, diphenylcyclopropenone, or minoxidil:
- Treatment with systemic immunosuppressive medications including but not limited to methotrexate, cyclosporine, and azathioprine; chloroquine derivatives; Janus kinase inhibitors (ruxolitinib, tofacitinib, etc), etanercept; or biologics (adalimumab, atlizumab, canakinumab, certolizumab, fontolizumab, golimumab, infliximab, mepolizumab, rituximab, secukinumab, tocilizumab, ustekinumab);
- Use of strong CYP3A4 inhibitors (such as, but not limited to clarithromycin, conivaptan, grapefruit juice, indinavir, itraconazole, ketoconazole, lopinavir/ritonavir, mibefradil, nefazodone, nelfinavir, posaconazole, saquinavir, telaprevir, telithromycin, voriconazole, or fluconazole);
- Use of strong CYP3A4 inducers (such as, but not limited to barbiturates, carbamazepine, efavirenz, glucocorticoids, modafinil, nevirapine, oxcarbazepine, phenobarbital, phenytoin, pioglitazone, rifabutin, rifampin, St. John's Wort, or troglitazone).

• PUVA treatment, UV-B phototherapy (including tanning beds) or excimer laser, excessive sun exposure or use of tanning booths.

• Obtain hair transplants.

#### 9. STUDY ASSESSMENTS AND PROCEDURES

The schedule of assessments and procedures is presented in Table 1 should be referenced for details regarding the collection of each assessment at each visit.

### 9.1. Demographic Characteristics and Medical and Surgical History

Demographic characteristics (i.e., sex, ethnic origin, date of birth) will be collected at the Screening Visit, between Day -28 and -1, and detailed on the eCRF.

The patient's alopecia areata will be classified by the Investigator into one of three categories defined for this study:

- 1) Alopecia areata: patchy type hair loss,
- 2) Alopecia totalis or universalis: complete hair loss on the scalp with or without body hair loss,
- 3) Alopecia ophiasis: band-like hair loss limited to the periphery of the scalp along the back of the hair line in the occipital region and possibly extending over each ear in temporal regions.

Key criteria that distinguish alopecia areata from other forms of hair loss may include abrupt onset of disease, a history of recurrence and spontaneous remission, response to topical or intralesional steroid treatment, and distribution of hair loss pattern. Care must be taken during the evaluation to assess for other causes of hair loss such as trichotillomania, or scarring alopecia and other forms of non-scarring alopecia. Evidence of thinning hair should be distinguished from pattern hair loss or telogen effluvium and evidence of inflammation should be investigated to rule out infection, as appropriate.

Thorough medical history, including current medications, nail and facial hair involvement, comorbidities, serious infection history and exposure risk, including HIV, as well as history or vaccination against herpes zoster will be collected at the Screening Visit, and at the Randomization Visit on Day 1.

Medical history should be thoroughly probed for potential exposure to serious infections such as HIV, history or vaccination against herpes zoster, as well as cancer risk due to the potential immunosuppressive properties of CTP-543 and known adverse events associated with JAK inhibitors.

### 9.2. Severity of Alopecia Tool (SALT)

The SALT score was introduced as part of investigative guidelines published by the National Alopecia Areata Foundation [Olsen 2004]. The SALT is a measure of hair absence that quantifies the amount of scalp surface without hair in a pre-specified quadrant of the scalp (right side, top, left side, back), that is further summed after applying a quadrant-specific multiplier indicative of scalp surface area contribution, to provide an overall score of total hair loss. The SALT assessment will occur via live examination of the patient by the investigator during clinic visits.

SALT will be used to determine efficacy for the study. To reduce variability, one rater, whenever possible, should perform the SALT assessment for the patient for the duration of the study. All investigators using the SALT should be trained prior to use. Please consult the associated Site Study Manual for additional details regarding SALT scoring and training

Concert Pharmaceuticals, Inc.

requirements for this study. An example of the SALT assessment tool is provided in Appendix 16.1.

### 9.3. Photographs

Sites may take photographs of their patient's scalps to provide visual support of Baseline assessment of SALT as well as potential changes in SALT scores throughout the study. No analyses of photographs will occur. The photographs will correspond to the 4 defined quadrants of the SALT assessment and will be taken when SALT assessments are performed.

For those patients with eye and nail involvement in their alopecia areata phenotype, a photograph of the eyes and hands for eyelash/eyebrow and nail involvement, respectively, may be taken to document potential changes throughout the study compared to Baseline. No formal analyses of photographs will occur.

